2.2.1. Primary Estimand

The primary estimand is the treatment effect of PF-07055480 compared to routine prophylaxis with respect to Total ABR (treated and untreated bleeds) after prior prophylaxis treatment is stopped following infusion, from Week 12 [Day 78] through at least 15 months (up to data cutoff) postinfusion.

The corresponding estimand attributes are provided in Table 3 below.

Table 3. Attributes of Primary Estimand

Estimand Attribute	Description
Population	Male participants ≥ 18 years of age with moderately severe to severe hemophilia A (FVIII:C $\leq 1\%$), who have tested negative for anti-AAV6 nAb and have no medical history of FVIII inhibitor.
Variable	Total ABR (treated and untreated bleedings) from Week 12 [Day 78] through at least 15 months (up to data cutoff) post PF-07055480 infusion.
Intercurrent Event	
 • Any data after the resumption of FVIII prophylaxis regimen (if necessary) will be excluded. • Data after study discontinuation will not be imputed.
Population-Level Summary	Total ABR post PF-07055480 infusion will be compared to participants' Total ABR on prior FVIII prophylaxis regimen using a repeated measure negative binomial regression model. Model-based estimated difference in mean Total ABR and the 95% CI will be reported. In addition, percent reduction in mean Total ABR and the corresponding 95% CI will be estimated.

Because no more than a single dose of study intervention will be administered during the study, there should be no treatment discontinuations. If it is determined by the investigator that a participant should resume routine prophylaxis post PF-07055480 infusion, date and

reason of investigator decision to resume FVIII prophylaxis will be collected in the eCRF, and this date will be considered as the date of FVIII prophylaxis resumption.

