6.5.2. Disallowed Therapy

The following concomitant medications are not permitted during the study:

- Blood products such as RBCs, platelets, and fresh frozen plasma, except as required during a surgery or as clinically indicated in the setting of an emergency.
- Medications that may increase the risk of bleeding such as anti-platelet agents (eg, aspirin, clopidogrel); NSAIDs (eg, ibuprofen, naproxen); anticoagulants (eg, warfarin, apixaban), except for the management of FVIII activity increases >ULN (please also refer to [Section 6.5.1](#) and the “Management Guide for Elevated Factor VIII Activity Levels”). Low dose aspirin (<100 mg/day) and PRN use of NSAIDs are allowed where medically necessary. Please contact the sponsor’s medical monitor if there are any questions regarding the use of medications that may prolong bleeding.
- Where possible, medications with known hepatotoxicity should be avoided. The investigator should inform the sponsor’s medical monitor of any plan to administer a medication with known hepatotoxicity.
- Concomitant use of another investigational therapy (for guidance about COVID-19 vaccination, refer to [Appendix 9 \[Section 10.9.6\]](#)); concurrent participation in another interventional clinical study is not allowed.
- Bypassing agents (eg, factor VIIa, activated prothrombin complex concentrate) and nonfactor treatment (eg, emicizumab), except in situations where it is medically necessitated. Antifibrinolytics (aminocaproic acid or tranexamic acid) are also disallowed.

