8.2.7.2. Analysis of FVIII Inhibitor

During all study periods, blood samples will be collected for measurement of inhibitory antibodies against FVIII (inhibitors) as specified in the SoA section of the protocol.

The Bethesda-Nijmegen assay will be used. One BU is defined as the amount of inhibitor that results in 50% residual FVIII:C activity.

Both de novo inhibitors and clinically significant de novo inhibitors will be assessed and are defined based on the following criteria.

- A de novo FVIII inhibitor is defined as a positive central laboratory inhibitor result (inhibitor assay result > 0.6 BU) by the Nijmegen method of the Bethesda assay, in an individual with no prior history of FVIII inhibitors, that is confirmed in a second separately drawn specimen, at least 6 weeks later, that is also assayed at the central laboratory. A local laboratory result indicating possible presence of an inhibitor will prompt an unplanned inhibitor assessment at the central laboratory.
- A de novo inhibitor will be deemed clinically relevant if the occurrence is associated with either complete loss of previously attained FVIII transgene expression (return to baseline FVIII activity level) or the need for the participant to administer non-FVIII coagulation factor products (by-pass agents) in order to achieve efficacy when treating breakthrough bleeding episodes.

In the event of a confirmed inhibitor level for a participant, the study will be paused (no additional participant will be treated) until the circumstances for occurrence of the event are assessed and until notification of regulatory agencies if required. The trial re-start will only be possible after Regulatory Authority approval via substantial amendment, where applicable based on local/regional regulatory requirements.

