2.2.2. Secondary Estimands

The secondary estimands are the treatment effect of PF-07055480 with respect to FVIII activity level $> 5\%$ at 15 months postinfusion and the treatment effect compared to routine prophylaxis with respect to Treated ABR after prior prophylaxis treatment is stopped following infusion, from Week 12 [Day 78] through at least 15 months (up to data cutoff) postinfusion. Throughout the SAP '15 months' corresponds to '65 weeks' for analysis purposes.

The secondary estimands include the following 4 attributes as described in Table 4 and Table 5 below.

Table 4. Attributes of Secondary Estimand –FVIII activity level $> 5\%$

Estimand Attribute	Description
Population	Male participants ≥ 18 years of age with moderately severe to severe hemophilia A (FVIII:C $\leq 1\%$), who have tested negative for anti-AAV6 nAb and have no medical history of FVIII inhibitor.
Variable	FVIII activity level $> 5\%$ at 15 months (65 weeks) post PF-07055480 infusion.
Intercurrent Event	
 Any sample taken within 72 hours for standard half-life or 120 hours for extended half-life products after administering exogenous FVIII replacement therapy for any purpose (including treatment of bleeding or prevention purposes) will be excluded from the assessment of FVIII activity post PF-07055480 infusion. Any data after the resumption of FVIII prophylaxis regimen (if necessary) will be excluded. Participants who resume prophylaxis regimen prior to Month 15 postinfusion will be considered as having FVIII activity level $\leq 5\%$. Participants who discontinue from the study before Month 15 will be considered as having FVIII activity level $\leq 5\%$.
Population-Level Summary	The percentage of participants with FVIII activity level $> 5\%$ will be calculated and compared with the null hypothesis of percentage $\leq 68\%$ using an exact test for binomial proportion.

Table 5. Attributes of Secondary Estimand - Treated ABR

Estimand Attribute	Description
Population	Male participants ≥ 18 years of age with moderately severe to severe hemophilia A (FVIII:C $\leq 1\%$), who have tested negative for anti-AAV6 nAb and have no medical history of FVIII inhibitor.
Variable	Treated ABR from Week 12 [Day 78] through at least 15 months (up to data cutoff) post PF-07055480 infusion.

Estimand Attribute	Description

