3.2.3. Annualized Infusion Rate (AIR) of Exogenous FVIII

AIR of exogenous FVIII replacement following PF-07055480 infusion from Week 12 [Day 78] through at least 15 months (up to data cutoff) after PF-07055480 infusion is considered as a secondary endpoint and will be compared with AIR during prior FVIII prophylaxis replacement regimen.

All infusions during the observation time period for any purpose (to treat bleeding, for preventive purpose, perioperative, or if FVIII prophylaxis regimen is resumed) will be included in the calculation of AIR. AIR data after PF-07055480 infusion will additionally be analyzed for the yearly intervals as well as cumulative follow-up intervals as separate secondary endpoints.

For participants with incomplete data for the entire yearly time period, including participants who discontinued prior to completing the study, all data during that period will be annualized and summarized utilizing the number of days of follow-up during the given time period. AIR for each participant will be calculated as below:

$$\text{AIR} = \frac{(\text{Number of infusions for any purpose during the given time period}) \times 365.25}{(\text{Number of days of follow-up in the given time period})}$$

Same as explained in [Section 3.1.1](#), the follow-up period will exclude the first 11 weeks (77 days). The denominator in the above calculation for postinfusion up to data cutoff, Month 15 interval and cumulative follow-up intervals will be [the last date in the given time period – (Date of PF-07055480 infusion) – 77 days +1]. If the participant discontinues from study before the end of the prespecified time period, the last date in the given time period will be the date of study discontinuation.

If a participant has to resume FVIII prophylaxis treatment, prophylaxis FVIII infusion data will not have to be reported on the eDiary (or conveyed to the study site staff on a contemporaneous basis) after Week 78 (Month 18). The eDiary will continue to collect bleeds and non-prophylactic infusions (e.g., on-demand and preventative) throughout the course of the study. The prophylaxis infusion data will be derived from the prescribed FVIII product information and included in the AIR calculation.

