Appendix 1.4. Additional US-specific Analyses

Total ABR:

Supplementary analysis: Repeat the same analysis model and summary for the main analysis as described in [Section 6.1.1.1](#) on the Total ABR from Week 12 through data cutoff using the ‘Dosed’ population regardless of the length of follow-up preinfusion or postinfusion. In addition, the imputation rule per given event below in Table 10 will be applied.

Table 10. Imputation Rules for US-Specific Analysis of Total ABR

Event	Imputation Rule
Resumption of prophylaxis regimen	The Total ABR post prophylaxis resumption date through data cutoff will be imputed with 35.
Taking FVIII infusions post PF-07055480 infusion for a time period in a manner similar to prophylaxis regimen (Note: these events will be identified based on clinical review.)	The Total ABR during this period will be imputed with 35.

If a participant resumes prophylaxis regimen and then later discontinues from the study prior to data cutoff, his Total ABR post prophylaxis resumption data through data cutoff will be imputed with 35 (i.e., the imputation rule will be applied for the period from study discontinuation to data cutoff).

The corresponding supplementary estimand is the treatment effect of PF-07055480 compared to routine prophylaxis with respect to Total ABR (treated and untreated bleeds) after prior prophylaxis treatment is stopped following infusion, from Week 12 [Day 78] through data cutoff.

Table 11. Supplementary Estimand of Total ABR

Estimand Attribute	Description
Population	Male participants ≥ 18 years of age with moderately severe to severe hemophilia A (FVIII:C $\leq 1\%$), who have tested negative for anti-AAV6 nAb and have no medical history of FVIII inhibitor.
Variable	Total ABR (treated and untreated bleedings) from Week 12 [Day 78] through data cutoff post PF-07055480 infusion.
Intercurrent Event	
 • Data post prophylaxis resumption date through data cutoff will be imputed. • Data during a time period when the participant was taking FVIII infusion in a manner similar to prophylaxis regimen will be imputed. • Data after study discontinuation will not be imputed unless prophylaxis was resumed prior to discontinuation.

Estimand Attribute	Description

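### The rescue rules are triggered only by resumed FVIII prophylaxis, so starting a nonfactor product or bypassing agent as prophylaxis has no analysis rule

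*SAP*

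**What the plan says.** **Use of non-FVIII products.** Protocol Section 6.5.2 lists as disallowed "Bypassing agents (eg, factor VIIa, activated prothrombin complex concentrate) and nonfactor treatment (eg, emicizumab), except in situations where it is medically necessitated". The exception is not limited to treating a bleed.

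**Rules triggered by resumption.**
- Total and Treated ABR (SAP Tables 3 and 5): "Any data after the resumption of FVIII prophylaxis regimen (if necessary) will be excluded". The date comes from the investigator's form: the "reason of investigator decision to resume FVIII prophylaxis will be collected in the eCRF, and this date will be considered as the date of FVIII" resumption.
- ABR denominator (SAP Section 3.1.1): it ends at data cutoff, the day before resumption, or discontinuation, whichever is earliest.
- FVIII activity at Month 15 (SAP Table 4): "Participants who resume prophylaxis regimen prior to Month 15 postinfusion will be considered as having FVIII activity level" of 5% or less. SAP Sections 3.2.1, 3.2.4 and 3.2.5 replace activity after resumption with 0.9%. The last two do the same after discontinuation for lack of efficacy.
- US-specific analyses (SAP Table 10): "The Total ABR post prophylaxis resumption date through data cutoff will be imputed with 35". A second trigger covers FVIII infusions taken in a prophylaxis-like pattern.

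**Other relevant text.** AIR (SAP Section 3.2.3) counts "All infusions during the observation time period for any purpose", but only of exogenous FVIII. The treatment-failure listing (SAP Section 6.1.1.3) has fields for FVIII infusions and for prophylaxis resumption, and none for non-FVIII therapy.

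**The concern.** Two participants with the same loss of effect would be analysed differently according to the product used afterwards. The one who goes back to FVIII prophylaxis leaves the ABR analysis on that date, counts as a non-responder on FVIII activity if this happens before Month 15, and receives 35 bleeds/year in the US-specific analyses. The one who starts emicizumab or a bypassing agent as prophylaxis stays in the ABR analysis, so bleeds prevented by the new product are credited to PF-07055480. He is not scored at 5% or less, or set to 0.9%, by rule, and he is not imputed at 35. In an open-label, single-arm trial the result should not depend on that choice, and it should not be left to a decision taken after the case has been seen.

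**Working it through.** **1. Does the looser wording close the gap?** Some rules say only prophylaxis regimen, without naming FVIII: the ABR denominator, the 5% rule and the first row of SAP Table 10. Three protocol passages stop this from covering a non-FVIII switch. Appendix 7 defines prophylaxis as scheduled factor replacement. Section 6.5.1 says that what may be resumed is the treatment used before gene therapy. Under inclusion criterion 2, that was FVIII prophylaxis for everyone. A bypassing agent might be argued to be factor replacement, but starting one is not a resumption. No other passage supplies a rule.

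**2. Inputs from the documents.** At least 50 participants, margin 3.0, assumed Total ABR of 5 before and 2 after infusion, correlation 0.2 (Protocol Section 9.2); Total ABR on emicizumab of 2.5 without and 5.5 with inhibitors (Protocol Table 3); imputed rate 35 (SAP Table 10). Assumptions made here: equal follow-up, and the number, timing and bleeding rates of switchers.

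**3. The plan's own power figure.** The assumed difference is 2 − 5 = −3, which is 6 below the margin. Power of 95% with 50 participants needs a standard deviation of the paired difference of at most 6 × √50 / (1.960 + 1.645) = 11.77. A simulation of 5,000 samples, with 0.5 year before and 1.035 years after infusion, gave 100% power at dispersion 0.5 to 2, 99.7% at 4 and 97.0% at 6. The stated figure of at least 95% is reproduced over that range (the documents give no dispersion). The present point does not rest on it.

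**4. US-specific analyses.** The change in the mean per full-window switcher is (35 − r)/50, where r is his rate on the new product.
- r = 2.5: (35 − 2.5)/50 = 0.65, and 0.65/3.0 = 22% of the margin.
- r = 5.5: (35 − 5.5)/50 = 0.59, and 0.59/3.0 = 20%.
- A switch halfway through the window halves these, to about 0.33 and 0.30.

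For k full-window switchers among 50, with the others at 2 bleeds/year:

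| k | Imputed at 35: ((50 − k) × 2 + 35k)/50 | As written, at 2.5: ((50 − k) × 2 + 2.5k)/50 |
|---|---|---|
| 1 | 2.66 | 2.01 |
| 3 | 3.98 | 2.03 |
| 5 | 5.30 | 2.05 |

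**5. Main analysis.** Suppose one participant bleeds at 12/year for the first quarter of the window and at 2.5/year after switching.
- Unweighted mean of participant rates: his own ABR is 12 if later time is excluded and 0.25 × 12 + 0.75 × 2.5 = 4.875 if it is counted. Counting lowers the mean of 50 by (12 − 4.875)/50 = 0.14, under 5% of the margin.
- Exposure-weighted rate: excluded, (49 × 2 + 0.25 × 12)/49.25 = 2.051; counted, (49 × 2 + 0.25 × 12 + 0.75 × 2.5)/50 = 2.058. Counting raises the rate by 0.007.

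With an identity link and negative binomial variance, under working independence, each participant's rate is weighted in proportion to t/(1 + κβt), where t is follow-up time, β the rate and κ the dispersion. That lies between the two cases above, so the sign depends on a dispersion that is not given and on the rates before and after the switch.

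**6. FVIII activity above 5%.** With 50 participants and a null of 68%, 41 responders give one-sided p = 0.0206 and 40 give p = 0.0437. This agrees with the SAP's statement that rejection needs more than 80%. One participant can therefore decide the test, but the missing rule affects only a switcher whose measured activity at Weeks 63 to 67 is still above 5%.

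**The case against.** The strongest reply is that these switches should be rare. The products are disallowed by default, the exception does not mention prophylaxis, and the stated course for lack of efficacy is to return to the previous treatment. This stands as a limit on frequency, which the documents do not give. It does not supply a rule for a case that the exception allows.

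A reader might infer a favourable bias in the primary test and throughout the testing sequence. The documents do not support that. The main analysis excludes data after resumption and does not impute them, the illustration moves in opposite directions under the two weightings, and both emicizumab rates in Protocol Table 3 exceed the assumed 2 bleeds/year after gene therapy.

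A reader might also infer that AIR and FVIII consumption become zero. They do not: FVIII given from Day 78 until the switch, or for later bleeds, still counts. The endpoint is use of exogenous FVIII, so recording none when none is used is accurate.

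Protocol Section 8.2.7.2 might be taken to foresee bypassing agents as prophylaxis, since it refers to "the need for the participant to administer non-FVIII coagulation factor products (by-pass agents"). That sentence goes on to the treatment of breakthrough bleeds. Only the protocol's risk table mentions using them to prevent bleeding.

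Finally, the Evaluable population removes major protocol deviations, and the treatment-failure listing is reviewed clinically. Use under the exception is not in itself a deviation, the Evaluable analysis carries no hypothesis test, and the listing lacks the relevant field.

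**Conclusion.** The gap is real and follows from the wording. It matters most in the US-specific analyses, which SAP Appendix 2 says carry hypothesis testing. The figure of 0.59 to 0.65 bleeds/year per switcher is an upper illustration: it assumes 50 equally weighted participants, a switch lasting the whole window from Day 78, and the emicizumab rates in Protocol Table 3. A few such participants are unlikely to change the main noninferiority conclusion. For FVIII activity, the responder endpoint is touched only where measured activity remains above 5%. The by-visit summaries and the Week 12 to Month 15 mean would use measured values in place of 0.9%. This should be corrected, but it does not undermine the primary analysis.

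**What to change.** In SAP Tables 3, 4, 5, 10 and 11, SAP Sections 3.1.1, 3.2.1, 3.2.4 and 3.2.5, and Protocol Sections 3 and 9.1.1, define the intercurrent event as the start of any bleeding prophylaxis: resumed FVIII, a bypassing agent or a nonfactor product. Apply the existing ABR exclusion, the 5%-or-less scoring, the 0.9% replacement and the imputation of 35 from that date.

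Record the start date throughout follow-up. Protocol Section 6.5 collects all concomitant therapy only to Week 104 and afterwards only therapy associated with reported adverse events, so existing collection is not enough. Add a non-FVIII therapy field to the treatment-failure listing.

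Keep AIR and annualized FVIII consumption as defined and list these participants. A sensitivity analysis that carries their preinfusion rate forward is optional.

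The change concerns analysis only and alters no rule on treatment. It costs wording changes, one extra data field, and slightly less favourable estimates if such cases occur. If none occur, no result changes.

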2.2.2. Secondary Estimands

The secondary estimands are the treatment effect of PF-07055480 with respect to FVIII activity level $> 5\%$ at 15 months postinfusion and the treatment effect compared to routine prophylaxis with respect to Treated ABR after prior prophylaxis treatment is stopped following infusion, from Week 12 [Day 78] through at least 15 months (up to data cutoff) postinfusion. Throughout the SAP '15 months' corresponds to '65 weeks' for analysis purposes.

The secondary estimands include the following 4 attributes as described in Table 4 and Table 5 below.

Table 4. Attributes of Secondary Estimand –FVIII activity level $> 5\%$

Estimand Attribute	Description
Population	Male participants ≥ 18 years of age with moderately severe to severe hemophilia A (FVIII:C $\leq 1\%$), who have tested negative for anti-AAV6 nAb and have no medical history of FVIII inhibitor.
Variable	FVIII activity level $> 5\%$ at 15 months (65 weeks) post PF-07055480 infusion.
Intercurrent Event	
 Any sample taken within 72 hours for standard half-life or 120 hours for extended half-life products after administering exogenous FVIII replacement therapy for any purpose (including treatment of bleeding or prevention purposes) will be excluded from the assessment of FVIII activity post PF-07055480 infusion. Any data after the resumption of FVIII prophylaxis regimen (if necessary) will be excluded. Participants who resume prophylaxis regimen prior to Month 15 postinfusion will be considered as having FVIII activity level $\leq 5\%$. Participants who discontinue from the study before Month 15 will be considered as having FVIII activity level $\leq 5\%$.
Population-Level Summary	The percentage of participants with FVIII activity level $> 5\%$ will be calculated and compared with the null hypothesis of percentage $\leq 68\%$ using an exact test for binomial proportion.

Table 5. Attributes of Secondary Estimand - Treated ABR

Estimand Attribute	Description
Population	Male participants ≥ 18 years of age with moderately severe to severe hemophilia A (FVIII:C $\leq 1\%$), who have tested negative for anti-AAV6 nAb and have no medical history of FVIII inhibitor.
Variable	Treated ABR from Week 12 [Day 78] through at least 15 months (up to data cutoff) post PF-07055480 infusion.

Estimand Attribute	Description
Intercurrent Event	
 Any data after the resumption of FVIII prophylaxis regimen (if necessary) will be excluded. Data after study discontinuation will not be imputed.
Population-Level Summary	Treated ABR post PF-07055480 infusion will be compared to participants' Treated ABR on prior FVIII prophylaxis regimen using a repeated measures negative binomial regression model. Model-based estimated difference in mean Treated ABR and the 95% CI will be reported. In addition, percent reduction in mean Treated ABR and the corresponding 95% CI will be estimated.

